Effective Screening for Pain Study

NCT01816763

July 2018

Abstract

Objectives: The overall objective of our mixed method study is to evaluate a strategy to improve the quality and clinical usefulness of ‘the 5th Vital Sign’ in VA primary care. We will formatively evaluate experiences with and implementation of the *enhanced pain screening approaches* (patient self administered computer aided) including clinician perspectives on the use of pain screening to guide management. Our specific aims are to:

Aim 1. Characterize primary care team and Veteran patient perspectives on enhanced pain screening approaches compared with usual pain screening re., clinical usefulness and how to use skills, roles, and tasks of multidisciplinary clinicians and consultants to optimize pain care. Interviews and focus groups will inform development of the screening interface. **Aim 2.** Evaluate in a three-arm RCT the effects of enhanced pain screening approaches using the PEG (Arm 1), the ‘NRS pain now (Arm 2), compared with DVPRS (Arm 3) followed by usual clinician-assessed pain screening, on the detection of patient pain as well as feasibility, acceptability, and experiences with (e.g., pain missingness), patient-reported tablet-based pain assessment using quantitative patient screening outcomes, and interviews with patients, clinic, and facility staff **Research Plan:** At three sites (VA GLA, Minneapolis, and Portland) we will conduct interviews and focus groups with primary care staff about their experiences with pain screening and how to link screening to management in order to inform development of an integrated enhanced pain screening approach (using PEG and NRS now and DVPRS) on a touchscreen together with survey questions on risk for under-assessed or under-treated pain. The integrated protocol will be installed on a touchscreen tablet to use in a 3 arm RCT to evaluate the optimal approach to pain screening, along with an evaluation of the implementation experience.

Methodology: Clinicians, clinic staff, and facility staff will be interviewed and multidisciplinary focus groups conducted at 3 sites to characterize the range of themes related to staff perspectives on patient reported versus clinician documented pain. Development of the enhanced pain screening protocol will account for clinician perspectives informed by qualitative input, as well as subsequent patient usability testing, and then the protocol integrated into a tablet interface will be subjected to an RCT that will be placed in primary care for selected Veterans to compare with staff administered pain screening. Veterans will be randomly allocated in a 1:1:1 ratio to the three arms and analyses will evaluate a variety of quantitative and qualitative outcomes. Veteran responses to the brief tablet based pain screening protocol and additional tablet based items will be linked to Veterans’ health data to evaluate feasibility and the association with social and clinical vulnerability (e.g., perhaps minority or cognitively impaired Veterans are particularly disadvantaged by the computer vs. in person pain assessments?). Linking to existing health data allows us to minimize the length and intrusiveness of the tablet based survey, while still assessing how social and clinical vulnerability is associated with screening measure and mode. Experience during the trial will inform implementation and be gathered through interviews with both patients and providers and clinic staff.

Results: This is a new project and results have not yet been obtained.

Significance: We will characterize how to best conduct pain screening including a direct comparison of patient reported to clinician documented pain, and selection of an optimal measure to improve clinician and patient centeredness of pain measurement (e.g., by considering the incorporation of function). This project will inform national VA implementation of a preferred measure and method.

Protocol Title: Effective Screening for Pain Protocol.....	3
1.0 Study Personnel.....	4
2.0 Introduction.....	7
3.0 Objectives.....	9
4.0 Resources and Personnel.....	10
5.0 Study Procedures.....	11
5.1 Study Design.....	11
Phase 1 Overview	11
Phase 1 procedures.....	11
a. Assess the usability of patient-self-administered pain assessment via tablet.....	13
Phase 2 Overview	14
A. Multisite RCT to test pain screening approaches via tablet:.....	14
1. Recruitment and Consenting.....	14
a. Participant Eligibility.....	14

2.0 Introduction

Despite the importance of pain and widespread interest in patient-centeredness, the VA remains exceptional in emphasizing and successfully making pain and its management a routine feature of the health record and a focus of care. Awareness of pain and efforts to improve pain management rest on the VA's '5th Vital Sign' – a policy and practice of nursing staff routinely screening for 'pain now' at every health encounter using a 0-10 Numeric Rating Scale (NRS) (1).

Our team's previous research on the VA's '5th Vital Sign' informs the specific design of the ESP study as well as the proposed research products. (5-7) Our evaluation of routine pain screening practice in the VA identified some important concerns that keep the VA's '5th Vital Sign' from living up to its full promise:

- The "fifth vital sign" measure of current pain intensity, demonstrates limited accuracy leading to only moderate correspondence (e.g., ROC of 0.76-0.8 in two studies) for chronic disabling pain measured with the Brief Pain Inventory (BPI) (5,10), and
- Nursing staff who deliver pain assessment in about 50% of cases use informal, unstructured pain queries (e.g., 'Is your knee good today?') rather than adhering to formal use of the 0-10 NRS leading to pain underestimation, despite efforts to standardize assessment (5), and
- Linkage is missing between the current pain screening approach and improved care—pain screening information is passively available but seldom used by busy providers who act on moderate to severe pain with augmented management in only about 15% of cases. (6,7)

Several alternatives to the current pain screening approach (e.g., nurse administered 'NRS pain now' improve the sensitivity and specificity of screening for chronic pain – the optimal measure being a three item scale incorporating intensity and emotional and physical interference (e.g., the PEG). (6,7) The PEG includes items that assess physical and emotional interference, and it is very similar to the gold standard BPI from which it is derived in sensitivity, specificity, and sensitivity to change in detecting clinically important, functionally impairing pain. (6)

A patient-reported approach (e.g., PRO) might be preferable to clinician screening, but these alternatives should be formally compared. On the one hand, nursing staff responsible for screening for the 'Fifth Vital Sign' screen informally which reduces screening sensitivity. (5) We found that nursing staff members' work experience, confidence in pain management, and use of informal rating contribute to pain screening variation. (11) Thus, by removing nursing staff rater variation, A PRO approach might improve standardization of the report. Other benefits could include scalability and sustainability over time including evolution consistent with automating aspects of care.

Although a PRO approach might reduce variation due to nursing staff rating factors, it could also increase variation by introducing unique issues including the specific items, mode, and context. For example, we also found in HELP-Vets that environmental context (e.g., a distracting or busy environment) contributed to pain screening variation, (11) and those could be worse depending on the physical environment of a tablet! Further underscoring the need to compare approaches, clinician documented pain could be less sensitive but more actionable (e.g., clinicians document the pain

they can do the most about), and some patients' who are challenged to self report (e.g., those with profound cognitive or visual impairment) might be best evaluated by a clinician.

In considering an enhanced pain screening solution, we will conduct a formative evaluation for more widespread implementation including consideration of the role of informatics and how to link screening-to management. (8,12) In the longer term, implementation success has to be framed in how screening improves patient outcomes – in the case of pain, through the use of meaningful metrics (e.g., functional), actionable treatment strategies, and multidisciplinary and generalist-specialist collaboration. Although it's unclear exactly how to link screening to management, clinicians need to be engaged to determine how screening information should be presented and integrated in workflow to facilitate patient outcomes.

Informatics offers an important focus in how to link screening to management. (12) Informatics leverages the electronic availability of the '5th Vital Sign' embodied in VA data systems. Although they have not been standardized or distributed in VA practices, informatics features of the VA-based trial on which the VA's national pain policy of 'stepped pain management' is based included treatment recommendations communicated through electronic alerts and email, 'order sets' based on treatment recommendations, and triggered consultations. (12,13) No specific research illuminates informatics design for pain management although features of effective alerts, clinical reminders, order support, and analogous applications are well described. (14-16) The ESP project will conduct preliminary work to characterize informatics solutions to link screening to management that can be experimentally evaluated in a subsequent study. The ESP project aims to conduct a naturalistic experiment of the use of pain screening and context that as closely as possible replicates daily VA primary care practice. The project aims to have minimal drop out because it will directly inform national implementation of a new routine pain screening process (a process that is used in approximately 30 million + health encounters annually). Representing the general population of veterans is particularly crucial for those Veterans who because of vulnerability might be both more likely to decline to participate, but are also those whose reports of pain might be most jeopardized by a move to computer based screening. (such as those with mental health conditions). The project is focused on implementation or how to roll out tablets without special research support; thus a broad variety of clinical and non-clinical staff will provide important input on how to make rollout of the tablets successful.

3.0 Objectives

The overall objective of our mixed method study is to evaluate a strategy to improve the quality and clinical usefulness of 'the 5th Vital Sign' in VA primary care. We will first develop a patient-self administered computer-aided pain assessment, then evaluate and refine the assessment using human-computer interaction laboratory usability testing. Next we will conduct a three site randomized controlled trial (RCT) to test a computer-based pain assessment protocol compared with usual pain screening. In the RCT we will evaluate three arms – one arm will use the PEG, a more sensitive screener including pain functional impairment, and a second arm will replicate the 'NRS now' allowing a direct comparison of patient-administered assessment vs. clinician assessed pain and a third arm will test the NRS at one week. All subjects will be screened with the '5th Vital Sign'. (allowing a three arm comparison of each of two computer based approaches vs. usual practice) Our specific aims are to:

Aim 1. Characterize primary care team perspectives on enhanced pain screening approaches compared with usual pain screening, including clinical usefulness and how to use skills, roles, and tasks of multidisciplinary primary care clinicians and consultants to optimize pain care. Additionally, we will try to understand Veterans' experiences with pain screening, assessment, and management (including use of opioid analgesics) in order to better link their actual experience with provider assessment and management practices. Interviews and focus groups will inform refinement of the items and screening interface; we will evaluate the interface including the PEG and 'NRS now' and the control arm for usability including among disabled veterans and for use in primary care.

Aim 2. Evaluate in a three-arm RCT the effects of enhanced pain screening approaches using a tablet and comparing the PEG, the 'NRS pain now', and usual clinician-assessed pain screening.

Hypothesis 2a: One of three enhanced pain screening approaches using the PEG, but not the 'NRS now' will be associated with improved detection of pain related disability **Hypothesis 2b:** Enhanced pain screening approaches vs. usual pain assessment will be associated with equally low missingness, Veterans, providers, and clinic and facility staff will characterize their experience with the enhanced screening protocol and important barriers, facilitators, and practical steps to inform implementation

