In general, we will solicit a visit-based sample of Veterans at each site so that we can ensure diversity in the population of Veterans and to minimize biases in our recruitment procedures. We plan to enroll approximately 650 participants among all three sites combined. We will recruit no more than 2000 respondents.

After a brief run-in phase, patients presenting in specified primary care clinics in the Palo Alto, Portland, and Minneapolis VAs will be asked to complete the survey on a tablet before vital signs are taken by clinic staff.

a. Participant Eligibility:

Veterans are eligible if they are attending a clinic visit in a participating primary care clinic and will have their vital signs taken as part of that visit and are not otherwise determined to be ineligible.

Veterans would be determined ineligible if they are:

- Severely visually impaired
- Incapable of rationale responses
- Physically unable to manipulate/control the tablet (unless a proxy is present and willing to input the Veteran's responses)

b. Recruitment

The primary recruitment will take place in the primary care clinics by trained research assistants approaching Veterans after they have checked in for their appointment. If a veteran expresses interest in participating, they will be informed of the study and screened for eligibility. All veterans approached by clinic staff will receive an anonymous study identification. Research staff will recruit in clinics for full or half-days selected from within the study enrollment window. A Research Assistants will use a 'Next Available' method of randomizing which Veterans will be approached (i.e., When the R.A. is ready to begin/resume recruitment the next patient that completes the check in process for the clinic will be approached.)

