If possible, research staff will attend a local clinic staff meeting to briefly inform the staff of the study. By partnering with local clinic leadership, we plan to send emailed invitations to eligible staff members. A log of all contact attempts will be maintained and after a maximum of 3 contact attempts the staff member will be removed from the contact list.

2. Consent Process:

Prior to the interview, a research staff member will verbally consent the participant. We have approval for a waiver of documentation of informed consent. Date of consent and person obtaining consent will be logged on the secured Excel sheets stored on VA Palo Alto Servers.

3. Data Collection Procedures:

We will conduct up to 40 telephone interviews that will take approximately 20-30 minutes. The interviews will be audio recorded and later transcribed by a VA contracted transcription service. For interview questions/content please see the Provider Interview Protocol.

4. Data Security:

Any information linking identifiable information with an assigned participant ID will be located on the secured Excel sheets. These Excel sheets will be secured and stored as previously mentioned under Phase 2: a: Data Security.

Audio files will be uploaded to the secured server located at VA Palo Alto. The audio Files will be saved using the assigned participant id. Audio files and de-identified transcripts will be transferred between VA servers and the transcriptions service via an approved secured FTP server.

Figure 1: Estimated enrollment scheme for ESP

Due to randomization the proposed enrollment algorithm will allow analytic comparison of each assessment measure / mode to the other. The table below specifies the Arm to Arm comparisons but the outcomes of each comparison are ‘clinically significant pain’ defined as pain that is moderate to severe, pain that is associated with disability, or unmet need for additional management.

Main comparison (s) of interest		Arm (s)	Comment
1	Tablet: PEG vs. NRS 1 week vs. DVPRS	1 to 2 to 3 tablet comparison	Baseline arm to arm difference

Table 1: Main analytic comparisons by screening measure and mode for outcomes of detection of pain, detection of moderate / severe pain (clinically relevant), pain associated with disability and unmet needs for treatment

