5.3 Study Evaluations/Data Analysis

Phase	Data Type	Source	Outcome	Analyses	Comment
1	Qualitative	Multidisciplinary providers, clinic staff, and Veterans	n/a	Grounded theory	Characterize screening information use in care
			management		
1	Quantitative	Patient	Pain-related disability, detection	By intervention arm*	At screening encounter

1&2	Quantitative	Patient, linked to VA health data for Veteran demographics and clinical factors	Pain missingness,	By intervention arm*	At screening encounter
2	Qualitative	Provider, patient	Satisfaction and experiences with screening including implementation	Grounded theory	Characterize experiences with the tablet and enhanced pain screening approaches

Outcome	Measure	Analysis	Model
Immediate pain related disability	NHIS pain-related disability	Arm 1,2,3 pairwise	Linear regression, adjusted for patient factors
Immediate pain missingness	NRS (nurse), NRS (tablet), PEG (tablet);	% missing pain ratings (Arm 1,2,3)	Logistic regression, adjusted for patient, rater (tablet perception), and environmental factors

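### Hypothesis 2a couples a PEG gain with a no-effect claim for the NRS, and the planned arm comparisons do not test it as worded

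*Protocol*

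**What the plan says.** **Hypothesis (Protocol 3.0).** Hypothesis 2a predicts that an enhanced screening approach "using the PEG, but not the 'NRS now' will be associated with improved detection of pain related disability". It gives no margin for what counts as no improvement.

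**What improvement is measured against (3.0).** The same section says "All subjects will be screened with the '5th Vital Sign", and explains that this allows the computer-based approaches to be compared with usual practice.

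**Planned contrasts (5.1, text above Table 1, and Table 1).** The text says "Due to randomization the proposed enrollment algorithm will allow analytic comparison of each assessment measure / mode to the other". Table 1 lists one main comparison, "1 to 2 to 3 tablet comparison", of PEG, NRS 1 week and DVPRS. Its caption includes detection of pain associated with disability among the outcomes.

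**Planned model (5.3, second table).** For pain-related disability the measure is the NHIS item, the analysis is "Arm 1,2,3 pairwise", and the model is "Linear regression, adjusted for patient factors". The first table in 5.3 lists detection as an outcome by arm but gives no model for it.

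**Size (5.1, Recruitment and Consenting).** "We plan to enroll approximately 650 participants among all three sites combined", allocated 1:1:1 according to the abstract.

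**The concern.** A prediction that one measure improves detection and another does not has two parts. The first can be supported by rejecting a null hypothesis. The second cannot, because failing to reject is not evidence of no gain unless the interval excludes a gain that matters. Nor does a significant PEG result beside a non-significant NRS result show that the PEG detects more than the NRS. Only a direct comparison of the two does.

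A direct comparison is planned, so the question is whether it answers Hypothesis 2a. If it does not, an analyst who wants to report on 2a is pushed back to comparing two significance statements. The abstract says the project will inform national implementation of a preferred measure and method, so a wrong reading of PEG against NRS would carry weight.

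**Working it through.** **1. Does the 5.3 model test detection?** The model regresses NHIS disability on arm. Disability is a characteristic the Veteran brings to the visit, it is recorded at the screening encounter, and no treatment comes between. Under randomization its expected mean is the same in all three arms, whether or not one screener is better. Apart from any priming by question order, the expected arm difference is zero even if the PEG finds every disabled Veteran and the NRS finds none. Detection is agreement between screener result and disability status, and that does not enter this model.

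**2. Does Table 1 test the named comparator?**

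| Place in protocol | Tablet arms |
|---|---|
| Abstract, Aim 2 | PEG; NRS now; DVPRS |
| 3.0 Objectives | PEG; NRS now; NRS at one week |
| 5.1, Tablet based survey content | PEG; NRS one week; DVPRS |
| 5.1, Table 1 | PEG; NRS 1 week; DVPRS |

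Table 1 does concern detection and is a direct contrast. Under the last two rows, however, no tablet arm uses the NRS-now that Hypothesis 2a names.

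**3. Would a direct contrast settle the NRS clause?** No. Finding the PEG better than the NRS leaves open whether the NRS improves on the nurse rating. That needs the NRS gain itself, with an interval.

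**4. What the significance pattern would cost if it were used.** Assume PEG and NRS have the same true gain over the nurse rating and each is tested at two-sided 5% with power p. The nurse rating is taken in every arm, so the two tests can be paired within separate arms and are then independent:

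P(PEG significant, NRS not) = p(1 − p)

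If both tests instead shared one comparator group (correlation 0.5), the probability comes from a bivariate normal distribution.

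| Assumed power p | Separate arms | Shared comparator |
|---|---|---|
| 30% | 0.21 | 0.14 |
| 50% | 0.25 | 0.17 |
| 70% | 0.21 | 0.14 |
| 80% | 0.16 | 0.11 |
| 90% | 0.09 | 0.07 |

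A direct two-sided 5% test favours the PEG by chance in 0.05/2 = 2.5%. A simulation of exact McNemar tests (assuming nurse sensitivity 60%, 30–50% of each arm disabled, latent correlation 0.5–0.8 and a true gain of 10 points for both) gave 17–25%. The protocol gives none of those inputs and does not specify a McNemar analysis.

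**5. What a direct contrast could show.** The text at hand gives no alpha, power or effect size for the 650, so there is no power figure to reproduce. Per arm, 650/3 ≈ 217. Assume 30%, 40% or 50% are disabled (about 65, 86 or 108 Veterans), true sensitivities of 80% and 70%, and a two-sided 5% test:

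- SE = √[(0.8×0.2 + 0.7×0.3)/n] = √(0.37/n)
- n = 65: SE 0.0755, z = 1.33, power Φ(1.33 − 1.96) ≈ 26%
- n = 86: SE 0.0656, z = 1.52, power Φ(1.52 − 1.96) ≈ 33%
- n = 108: SE 0.0585, z = 1.71, power Φ(1.71 − 1.96) ≈ 40%

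At n = 86 the 95% CI half-width is 1.96 × 0.0656 ≈ 13 percentage points.

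**The case against.** The strongest reply is that the faulty inference is nowhere in the protocol. Hypothesis 2a states a scientific expectation and attaches no decision rule. Section 5.1 says randomization permits each measure to be compared with the others, Table 1 lists exactly that comparison for detection outcomes, and 5.3 plans pairwise arm contrasts, which include PEG against NRS. A margin for no improvement could properly sit in a statistical analysis plan that is not shown. The error rates in step 4 describe an analysis that the protocol does not specify.

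Most of this stands. A reader might infer that 2a can be supported only by a non-significant NRS result, or that the trial will declare the PEG better on that basis. The documents do not support either inference: no such rule is stated and direct contrasts are planned. The absence of a margin is not in itself a finding.

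The reply does not reach steps 1 and 2. The wording of the hypothesis, the 5.3 model and the identity of the comparator are all fixed in the protocol, and they do not fit together. The one model given for pain-related disability does not measure detection, and the one contrast that does concern detection names a different NRS.

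**Conclusion.** The point holds in a limited form. Hypothesis 2a contains a no-effect clause that a difference test cannot confirm, and its usual-practice framing invites a significant-versus-non-significant reading. The planned direct comparisons would be the right remedy, but as written they do not test 2a. This follows from the text and from randomization and needs no numerical assumption.

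The size of the possible error is illustrative only: about 7–25% for the misleading pattern under equal true gains and assumed power of 30–90%, against 2.5% for a direct test. The change is worth making because it alters what the trial can conclude about PEG against NRS and needs no new data.

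**What to change.** 1. Restate Hypothesis 2a as a direct PEG-versus-NRS difference in detection of pain-related disability, in line with Table 1, and drop the clause that the NRS does not improve detection.
2. In 5.3, replace the regression of disability on arm with a between-arm comparison of detection: sensitivity at a stated cut-off (with specificity beside it) or AUC, against the reference measure, with a 95% CI. Name that reference once; the tablet survey content in 5.1 calls the Graded Chronic Pain Scale the gold standard, while 5.3 lists the NHIS item.
3. Reconcile the NRS version across the abstract, 3.0, the tablet survey content and Table 1, and use the same name in the hypothesis.
4. Report the NRS gain over the nurse rating as an estimate with a 95% CI. Do not call it no improvement because it is non-significant; make that claim only if the upper limit lies below a margin set before analysis.

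The cost is a reworded hypothesis, one changed table row and consistent arm labels. The drawback is that the direct contrast may be inconclusive, at 26–40% power for 80% versus 70% sensitivity under the assumptions in step 5, so a claim for the PEG becomes harder to make.
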